8. RESEARCH METHODS

8.1. Study Design

A prospective observational cohort study nested within the EuroSIDA study, using data from individual medical records from participating clinical sites will be conducted over a period of five years to meet the study objectives.

This study will be conducted through collaboration with EuroSIDA, a well-established, prospective observational cohort study of more than 13,000 individuals under active follow up in over 100 hospitals in 34 European countries, and Israel and Argentina [1].

For this non-interventional study, treatment and laboratory testing decisions will be made by the treating physician according to standard practice, taking into account the treatment history, individual characteristics, the approved SmPc for CAB+RPV oral and LA

formulations, contemporary regimen and local guideline or recommendations. All individuals who discontinue the regimen for any reason, will be followed for up to 48 months after discontinuation. The study protocol will be implemented by the EuroSIDA coordinating center.

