Descriptive analyses will compare those with and without virologic failure to assess any differences in baseline characteristics of the two groups. Detailed analysis of additional risk factors will be limited to persons with 6, 12 or 24 months of follow-up. Multivariable logistic regression models will investigate the factors associated with virologic failure at 6 months, 12 months and 24 months after CAB+RPV LA initiation. Potential explanatory variables are listed above. We will also investigate the impact of missed doses and use of oral bridging therapy by using the data collected via the CRF. Multivariate analyses will be performed when > 30 persons on CAB+RPV LA have virologic failure and analyses will be limited to persons with > 6-, 12- or 24-months follow-up. The model building strategy will follow EuroSIDA protocol and include variables significant in univariate analyses as well as *a priori* pre-specified variables of interest. Primary analysis for clinical effectiveness will include individuals on CAB+RPV LA, with VL of <50/copies/mL at regimen initiation. In addition, all the analyses will be conducted separately for individuals on CAB+RPV LA with VL of ≥50 copies/mL at regimen initiation.

Our primary analyses of virologic outcomes will censor follow-up at discontinuation of CAB+RPV LA, last visit or death, whichever occurs first, an on-treatment approach to analysis. Sensitivity analyses will use an intent to treat approach and virologic outcomes will be assessed regardless of regimen discontinuation.

We will perform additional sensitivity analysis limited to those who start CAB+RPV LA with resistance data available, to confirm no present or past evidence of viral resistance to, and no prior virological failure with agents of the NNRTI and INSTI class.

AIM 4. Monitor for resistance and next treatment response among individuals who switched off CAB+RPV LA regimen

Monitoring for resistance

Since this is a non-interventional study aiming to capture individual care in real world setting, the study will not mandate resistance testing following discontinuation of the regimen of interest. Health care providers following the local treatment guidelines decide

what laboratory and resistance tests are to be conducted. Data thus generated will be captured and analyzed by the study team.

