Descriptive statistics will describe and compare the ARV regimen individuals are switched to after discontinuation of CAB+RPV LA regimen. As resistance testing will not be common, we will describe the characteristics of those with and without resistance testing at virologic failure and again at virologic failure during the 12, 24, 36 and 48 months after switching regimens and use logistic regression to identify factors associated with resistance testing. Where more than 1 resistance test is available during the 12, 24, 36 and 48 months after stopping CAB+RPV LA regimen, cumulative resistance data will be collected and reported.

Study will monitor for resistance at virologic failure and again at virologic failure during the 12, 24, 36 and 48 months following the switch, where resistance data are available. Resistance patterns in those with resistance testing will be summarized. Depending on the number of resistance tests performed and amount of resistance detected, logistic regression will be used to identify factors associated with resistance to CAB+RPV LA. Potential explanatory variables are listed above including missed and delayed doses and use of bridging therapy.

Next treatment response

The study will describe virologic success at 12, 24, 36 and 48 months after discontinuation of CAB+RPV LA regimen, using virologic failure definition as described above. Given that this study involves persons in routine clinical care, and who may not attend clinic appointments every 12 months, a window of 12 weeks around the date in question will be used for virologic testing data. Thus, the proportion with virologic success at 12, 24, 36 and 48 months \pm 6 weeks will be used; and if none is available, the first measurement after 6 or 12 months will be used.

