Descriptive analyses will compare those with and without virologic success at 12, 24, 36 and 48 months after stopping the CAB+RPV LA regimen, as well as the next regimen started and time to start the next regimen following discontinuation of the regimen. If numbers allow for further analyses, multivariable logistic regression models will investigate the factors associated with virologic success at 12, 24, 36 and 48 months after switching off CAB+RPV LA regimen. Potential explanatory variables are listed above. Multivariate analyses will be performed when > 30 persons in the relevant treatment group have virologic success and analyses will be limited to persons with > 12 months follow-up. The model building strategy will follow EuroSIDA protocol and include variables significant in univariate analyses as well as *a priori* pre-specified variables of interest.

AIM 5. Evaluate the effectiveness of routine risk minimisation measures for regimen adherence, discontinuation due to incorrect route of administration and off-label use of CAB+RPV LA regimen

The purpose of this aim is to monitor to see if label guidance is adhered to, off label usage, adherence and discontinuation due to incorrect route of administration. This analysis on effectiveness of routine risk minimisation measures will be stratified for each region in the Eurosida cohort.

Analysis of off-label users – regimen combinations other than CAB+RPV LA (b -g in objective 1)

Descriptive Analysis:

As noted in Aim 1 above, analysis will be performed on the off-label users of CAB and/or RPV LA containing regimens. They will be characterized using demographics, clinical, immunologic and virologic characteristics at baseline (i.e. at initiation of regimen) stratified by different regimens noted in groups b-g above.

Adherence and Discontinuation:

Non-adherence to the dosing schedule and discontinuation due to incorrect route of administration will be assessed as described under Aim 2.

Clinical Outcomes:

Analysis will be conducted for the off-label users of CAB and/or RPV LA containing regimens separately to assess clinical outcome similar to description under Aim 3 above.

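### Aim 4 applies one > 12-month follow-up rule to models at 12, 24, 36 and 48 months, and its fallback viral load is not tied to the later time points

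*Protocol*

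**What the plan says.** All of this is in the Protocol.

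- **Models (Section 8.6, Aim 4, next treatment response).** The logistic models, to be fitted only if there are enough people, look for "factors associated with virologic success at 12, 24, 36 and 48 months after switching off CAB+RPV LA regimen". They are to be run once more than 30 persons in the relevant group have virologic success.
- **Entry rule, same paragraph.** For all four time points, "analyses will be limited to persons with > 12 months follow-up".
- **Outcome (Section 8.6, Aim 4).** Success is judged "using virologic failure definition as described above", which points to the confirmed-failure definition in Section 8.3.2. For timing, "a window of 12 weeks around the date in question will be used for virologic testing data", that is, six weeks either side. Failing that, "if none is available, the first measurement after 6 or 12 months will be used".
- **Aims 3 and 5 (Section 8.6).** For failure at 6, 12 and 24 months the rule follows the time point: "analyses will be limited to persons with > 6-, 12- or 24-months follow-up".
- **Follow-up and reporting.** Section 8.1 says that people who stop the regimen "will be followed for up to 48 months after discontinuation". Section 5 ends data collection in June 2026 (or five years after commercial availability), places the final report in September 2026, and adds a Supplemental Report timed to the last discontinuer completing four years. Section 8.5.2 describes data running to about 6-12 months before database close.

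**The concern.** A follow-up restriction on a model at a fixed time point should ensure that those in it could have been observed at that point. A > 12-month rule does this for month 12 but not for months 24, 36 or 48. On its own the loose threshold might do little harm, because a person with no viral load near month 48 would have no month-48 outcome. The fallback removes that protection: it supplies an outcome from soon after month 6 or 12 and does not require the measurement to lie near the time point being modelled.

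At stake is what the later models mean. A model labelled 48 months could consist largely of responses from the first year or so after the switch. The start date of the long-acting regimen and geographic region, both listed as covariates in Section 8.3.3, may track how long a person could be observed. They would then partly determine whether the outcome is an early or a late viral load, and could appear associated with success for that reason. A loose rule also makes the trigger of more than 30 successes easier to reach, so a late model could be run before enough late data exist.

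**Working it through.** The protocol gives no figure for this point, so there is none to reproduce. The check asks what share of the > 12-month set can have reached each later time point.

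**Inputs from the protocol.** Threshold > 12 months and time points 12, 24, 36 and 48 (Section 8.6). Study start June 2021 (estimated) and data collection to June 2026, so 60 months (Section 5). Database lag 6-12 months (Section 8.5.2).

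**Assumptions.** The protocol gives no discontinuation pattern and no loss rate. I take discontinuations as even over the 60 months and also show linearly rising and falling patterns. Loss to follow-up is 0%, or 5-10% a year. The follow-up clock is taken to start at discontinuation, which the text does not state. If it started at regimen initiation, the rule would restrict even less.

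**Step 1: final report, even discontinuation, no loss.** With data to month C, a person who stopped at month t has C − t months of follow-up. The share reaching month m among those with > 12 months is (C − m) / (C − 12).

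| Data to | Month 24 | Month 36 | Month 48 |
|---|---|---|---|
| June 2026 (C = 60) | 36/48 = 75% | 24/48 = 50% | 12/48 = 25% |
| 6-month lag (C = 54) | 30/42 = 71% | 18/42 = 43% | 6/42 = 14% |
| 12-month lag (C = 48) | 24/36 = 67% | 12/36 = 33% | 0/36 = 0% |

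**Step 2: other patterns, C = 60, month 48.**

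- Rising (weight t): 12² / 48² = 144/2304 = 6%.
- Falling (weight 60 − t): (60×12 − 12²/2) / (60×48 − 48²/2) = 648/1728 = 38%.
- Counting from the lower edge of the window (48 months less six weeks, about 46.6 months), the even case is (60 − 46.6)/48 = 28%, the rising case 8% and the falling case 41%.

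So fewer than half can have reached month 48 in each of these final-report scenarios.

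**Step 3: Supplemental Report.** Every discontinuer has had four years, so without loss the share is 100%. With yearly loss r, the share of the > 12-month set still followed at month 48 is (1 − r)³:

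- r = 5%: 0.95³ = 0.857, so 14% fall short.
- r = 10%: 0.90³ = 0.729, so 27% fall short.
- Half fall short only when (1 − r)³ = 0.5, that is r = 1 − 0.5^(1/3) = 21% a year.

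**Step 4: does the text let these people in?** Take a person with 13 months of follow-up and the 48-month model. The entry rule is met (13 > 12). There is no viral load at 48 months ± 6 weeks. The fallback then takes the first measurement after 6 or 12 months, which this person can have. Read literally, the person is included, with an outcome about three years too early. Under the matched rule of Aims 3 and 5 the same person would be excluded.

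**The case against.** The case on the other side is substantial.

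- **The Supplemental Report exists for 48-month data.** This stands. A reader might infer that most people in the 48-month analysis cannot have reached month 48, whenever it is run. The documents do not support that: it holds for the June 2026 cut under the assumptions shown, while at the Supplemental Report most would reach month 48 unless loss exceeded about 21% a year. However, the protocol does not reserve the later models for that report, and Section 8.8 itself expects loss over the four years.
- **The threshold does not create an outcome.** This also stands. A reader might infer that anyone who has not yet failed is counted as a success at month 48, so that late success is overstated by a calculable amount. Aim 4 does not say so: it uses a viral load in a window, with a fallback to a single measurement. An illustration that averages failure-free time to the end of each person's follow-up would describe a different rule. The route in is the fallback.
- **The restriction governs only conditional models.** Correct. Objective 4 is descriptive, and the proportions with success carry no > 12-month restriction. A reader should not infer that this restriction distorts them. The fallback wording, though, is written for those proportions too.
- **The fallback may be a drafting slip.** Probably so, since months 6 and 12 do not match Aim 4's own time points. That is a reason to correct it, not to rely on it being read charitably.
- **The detail could sit in an analysis plan.** An omission could. Here the protocol states a threshold and a fallback, and neither fits three of the four time points.

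**Conclusion.** The point holds as an error in two stated rules that act together. The > 12-month restriction does not match the 24-, 36- and 48-month models and departs, without a reason given, from the matched rule in Aims 3 and 5. The fallback lets an early viral load stand in at those time points.

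The size depends on when the models are run. At the final report a quarter of the > 12-month set, or fewer with the database lag, can have reached month 48 under even discontinuation. At the Supplemental Report the mismatch shrinks to losses to follow-up. These figures rest on assumed discontinuation patterns and loss rates and on a clock starting at discontinuation. They measure how many people could be misplaced, not the bias in any coefficient, whose size and direction the protocol does not allow one to calculate. The threshold affects only the conditional multivariable models. It is worth correcting because the repair is short and follows the protocol's own practice elsewhere.

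**What to change.** Make two changes in Section 8.6, Aim 4, next treatment response.

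1. Limit each model to persons with follow-up to its own time point (> 12, 24, 36 or 48 months respectively, allowing for the six-week window), as Aims 3 and 5 do. State that follow-up is counted from discontinuation of CAB+RPV LA.
2. Tie the fallback to the same time point: the first measurement after month 12, 24, 36 or 48, within a stated limit.

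Both are needed. With the first alone, a person followed past month 48 but without a viral load near it could still be scored on a value from soon after month 6 or 12.

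The cost is a few words in two sentences, and fewer persons in the 24- to 48-month models until the Supplemental Report. With data to June 2026 and even discontinuation, the set eligible for the 48-month model falls to 12/48 = 25% of the present one. At the Supplemental Report with no loss, both rules select the same people. No new data collection is needed.

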8.7. Quality control and Quality Assurance

Quality procedures are described in the "SOP for electronic data collection v4.1 (Autumn 2020)" (link) which includes the Quality Assurance measures for the data entry, as well as the Quality Control measures for the data entered. The results will be checked and quality assured by the statistics team responsible for the analysis in the first instance. The study results are then checked by a statistician from CHIP familiar with EuroSIDA and cohort studies but not directly involved in the CAB studies. The report will also be checked by the senior statistician and by the administrative team at CHIP for internal consistency and for continuity between successive years reports.

8.8. Limitations of the research methods

This is a study of routine clinical care and reflects treatment practice across the EuroSIDA consortium. Following up of study participants for 4 years after discontinuation of the CAB + RPV LA regimen will increase the potential for loss to follow up as would be expected, in a real world setting.

Not all clinical centres in EuroSIDA use a limit of detection for viremia of 50 copies/ml; 5-10 clinics continue to use an assay with a higher limit of detection. These centres are Eastern European countries where the uptake of CAB and/or RPV LA containing regimens are anticipated to be low. Individuals starting one of the regimens where the viral load as a limit of detection > 50 copies/ml will be excluded from analyses. We will compare those excluded by using a limit of detection for viremia of 50 copies/ml to those included.

Confounding by indication, whereby persons are selected for specific regimens, cannot be ruled out. Resistance testing is not routinely performed in many EuroSIDA clinics and the proportion of persons with resistance results may be low. Resistance testing may be targeted at specific groups of individuals and the results may not be applicable to the whole study population. While EuroSIDA has extensive experience at capturing data via REDCAP and CRFs, collecting this data retrospectively through additional CRFs might reduce data quality. Not all clinics will provide information, despite reminders, and the quality of the data might be lower or missing. Persons with or without data might be different, for example, persons who have died or lost to follow-up might not have data available. The results from this study should be interpreted cautiously, with careful consideration given to the limitations of the observational study design.

9. PROTECTION OF HUMAN SUBJECTS

9.1. Ethical approval and subject consent

The EuroSIDA cohort study is conducted according to the Declaration of Helsinki in its current version, the requirements of Good Clinical Practice (GCP) as defined in current EU GCP Directive, Human Subject Protection and Data Protection Acts or with the local law and regulation, whichever affords greater protection of human subjects.

Participating clinical sites will adhere to their appropriate local ethics approval procedures as requirement to be involved in the well-established and long-running EuroSIDA observational cohort. If required by the national or local ethical committee the persons enrolled in the study will sign the Individual Informed Consent form before any study related activities begin.

CONFIDENTIAL

Individuals are informed that data and plasma samples collected will be pseudonymized, stored safely and analysed in accordance with the scientific programme in EuroSIDA to study their HIV infection and associated diseases.

9.2. Subject confidentiality

Principles of medical confidentiality in relation to Study Subjects are maintained in accordance with GCP Guidelines and national regulations.

Individuals in the EuroSIDA study are de-identified and assigned a unique 7-digit PID number at the sites where they are enrolled. The de-coding list is held by the individual site in a safe location.

All study data is marked with this 7-digit PID number. Date of birth is collected as date, month and year of birth, and no unique person identifiers are present on data submitted to the coordinating centre. All data (hardcopies, computerised and samples) at the coordinating centre are stored and protected in accordance with current regulatory laws and approved by The Danish Data Protection Agency (DK: Datatilsynet, approval no. 2012-58-0004, RH-2018-15, I-Suite nr.: 6140)

The Principal Investigators and staff at the EuroSIDA centres will keep any information and data related to the EuroSIDA study provided by the coordinating centre, and all data and records generated in the course of conducting the study, confidential and will not use the information, data, or records for any purpose other than conducting the study.

Every reasonable step will be taken to protect the privacy of individual health information and to prevent misuse of this information. The individual records (paper/digital) may be seen by institutional Review Boards (IRBs) or Ethic Committees (ECs) who review the study to make sure it is ethically acceptable and by research staff and study monitors, and their designees.

Personal data shall not be disclosed to third parties save where this is required directly or indirectly to satisfy the requirements of the Protocol or for the purpose of monitoring or Safety Reporting. The identity of Study Subjects shall not be disclosed to third parties without prior written consent of the Study Subject and then only in accordance with the requirements of the applicable data protection act. Investigators and the EuroSIDA coordinating office shall ensure that only those of their officers and employees directly concerned with carrying out Study related activities are granted access to Confidential Information. All parties undertake not to disclose to any third party Confidential Information save where disclosure is required by a Regulatory Authority or by law, and not to make use of Confidential Information other than in accordance with this Protocol, unless the prior written consent been obtained.

10. MANAGEMENT AND REPORTING OF ADVERSE EVENTS/ADVERSE REACTIONS

There is no potential to collect individual level data on serious and non-serious adverse events (AEs), pregnancy exposures, device deficiencies and device related events or incidents related to any ViiV Healthcare product during the conduct of this research, as the minimum criteria needed to report AEs, pregnancy exposures, and incidents are not collected. Specifically, the data are insufficient to establish attribution between a potential safety event and an individual using a ViiV Healthcare product as the study design is to analyse deidentified, secondary data collected from individual medical records. Therefore, a study specific pharmacovigilance plan will not be developed.

11. PLANS FOR DISSEMINATING AND COMMUNICATING STUDY RESULTS

11.1. Milestones

This study-specific protocol will be submitted by 31 December 2020 for the EMA's review and endorsement. The study will start only after the protocol is approved by the EMA, and CAB+RPV LA is registered and commercially available in the relevant countries and is expected to continue through 2026 or later, for a total of five years of study period. Annual interim reports with cumulative data will be submitted and a final report is expected to be submitted in March 2027.

11.2. Target Audience

The target audience for these data includes healthcare providers, regulatory and health authorities.

